The PK Analysis Population is a subset of the SAF population and will consist of all participants who receive at least one dose of active IMP and provide at least one measurable post-dose concentration. A measurement below lower limit of quantification (BLQ) is considered a valid measurement. Participants will be analyzed according to the actual treatment they received. Subjects in this analysis population may not have taken prohibited medications/foods/fluids, and may not have experienced any diarrhea or vomiting after IMP administration.

Additional Subgroup Analysis Populations

Subgroup analyses will be performed on subgroups as defined below.

The final parameterization will be updated and fixed at the Data Review Meeting at the latest and documented in an amendment to this IAP if different from the following definition.

The following subgroups will be defined:

- Age
 - 4 to 6 years of age (Cohorts 1 and 4)
 - 2 to 3 years of age (Cohorts 2 and 4)
 - 3 to < 24 months of age (Cohorts 3 and 4)
- Gender

- Male
- Female
- Severity of infection (as assessed at Pre-screening [D-28 to D-1])
 - *S. mansoni* infection
 - Light infection: 1 - 99 eggs per gram of faeces
 - Moderate/heavy infection: ≥ 100 eggs per gram of faeces
 - *S. haematobium* infection
 - Light infection: < 50 eggs/10 mL of urine
 - Heavy infection: ≥ 50 eggs/10 mL of urine
- Note: In summary tables, *S. haematobium* heavy infection will be classified as Moderate /Heavy when being presented side-to-side with other cohorts.
- Trial center/country
 - PPD
 - [REDACTED]

9 General Specifications for Data Analyses

Study intervention groups

Study intervention groups are defined and labelled as Biltricide® and L-PZQ ODT.

Unless otherwise indicated all analyses will be presented separately for treatment groups. Specifically, Cohorts 1a and 1b will be presented separately in all tables. In general, in this IAP the term “cohorts” represents Cohorts 1, 2, 3 and 4, whereas the term “treatment groups” stands for Cohorts 1a, 1b, 2, 3, 4a and 4b with 4a and 4b representing Cohort 4 participants treated with 50 mg/kg and 60 mg/kg, respectively.

Data handling after cut-off date

Data (other than the date of death and the date last known to be alive) obtained after the cut-off will not be displayed in any listings or used for summary statistics, e.g. laboratory values of samples taken after data cut-off, AEs with onset date after data cutoff, etc. will not be included in any analysis or listing.

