As the known variability of systemic PZQ concentrations and PK parameters is high in adults, the number of participants in each PK subgroup is not based on statistical considerations but on feasibility assessments. Children weighing 5 kg to less than 7 kg will have 4 PK samples taken, children weighing 7 kg to less than 10 kg will have 7 PK samples taken, and children weighing 10 kg and above will have the full PK sampling scheme with 9 PK samples taken. For background information please see “Appendix 6 (in protocol) Pharmacokinetic Blood Sampling”. Participants assigned to the PK sub study should fast between the dosing and 4h post dosing.

Table 1 PK sampling times per body weight group

| Body weight range (kg) | Sampling times (hours) | | | | | | | | | |
|------------------------|------------------------|-----------|---|---|---|---|---|---|----|---|
| | Pre dose | Post dose | | | | | | | | |
| 5 to < 7 | No | 0.5 | 1 | 2 | 3 | - | - | - | - | - |
| 7 to < 10 | No | 0.5 | 1 | 2 | 3 | 4 | 6 | 8 | - | - |
| 10 and above | Yes | 0.5 | 1 | 2 | 3 | 4 | 6 | 8 | 12 | |

Note: the tolerance window of $\pm 10\%$ for the collections of timepoints.

Plasma concentrations will be tabulated and summarized using descriptive statistics. PK parameters will be calculated if possible as appropriate for the respective sampling schemes. All PK parameters will be calculated using standard non compartmental methods and the actual administered dose. Calculations will be performed using a validated software tool as described below.

The following PK parameters will be calculated, when appropriate:

Table 2 PK parameters

| Symbol | Definition |
|------------------|--|
| C_{\max} | Maximum observed concentration in plasma |
| AUC_{0-t} | Area under the plasma concentration-time curve (AUC) from time zero to the last sampling time at which the concentration is at or above the lower limit of quantification. Calculated using the mixed log linear trapezoidal rule (linear up, log down). |
| t_{\max} | Time to reach the maximum plasma concentration |
| t_{lag} | Time prior to the first measurable (non-zero) concentration |

PK parameters will be evaluated and listed for all participants who provide sufficient concentration time data.

Estimation of Individual PK Parameters:

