16.1.1 Presentation of PK Concentration and PK Parameter Data

16.1.1.1 Listings and Tables (PK Analysis Population)

Statistical analyses and descriptive summaries of pharmacokinetic data will be performed on the PK Analysis Population (PKP, as defined in Section 8.2). The following PK tables and listings will be produced:

- a) Descriptive Statistics of PK Concentration Data:
 - PK measurements will be descriptively summarized using: number of non-missing observations (N), arithmetic mean (Mean), standard deviation (SD), coefficient of variation (CV%), minimum (Min), median (Median) and maximum (Max).
 - Descriptive statistics will only be calculated for N>2 in which a measurement of <LLOQ represents a valid measurement

- Descriptive statistics of PK concentration data will be calculated using values with the same precision as the source data and rounded for reporting purposes only.
- The following conventions will be applied when reporting descriptive statistics of PK concentration data:
 - Mean, Min, Median, Max: 3 significant digits
 - SD: 4 significant digits
 - CV%: 1 decimal place

b) Descriptive Statistics of PK Parameter Data

- PK parameter data will be descriptively summarized using: number of non-missing observations (as N), arithmetic mean, standard deviation (SD), coefficient of variation (CV%), minimum, median, maximum, geometric mean (GeoMean), the geometric coefficient of variation (GeoCV) and the 95% confidence interval for the GeoMean (LCI 95% GM, UCI 95% GM). For time to reach maximum observed concentration (t_{max}), only n, minimum, median, and maximum will be reported.
- Descriptive statistics will only be calculated for a PK parameter when $N > 2$.
- PK parameters read directly from the measurements (i.e. C_{max}) will be reported with the same precision as the source data. All other PK parameters will be reported to 3 significant figures. In export datasets, as well as in the SDTM PP domain, PK parameters will be provided with full precision and will not be rounded. Descriptive statistics of PK parameter data will be calculated using full precision values and rounded for reporting purposes only.
- The following conventions will be applied when reporting descriptive statistics of PK parameter data:
 - Mean, Min, Median, Max, GeoMean, 95% CI: 3 significant digits
 - SD: 4 significant digits
 - CV%, GeoCV%: 1 decimal place

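### AUC0-t stops at 3, 8 or 12 h depending on body weight, yet it is summarised by treatment group without separating the sampling schemes

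*SAP*

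**What the plan says.** SAP 16.1, Table 2, defines AUC0-t as the area "from time zero to the last sampling time at which the concentration is at or above the lower limit of quantification", by a linear-up, log-down trapezoid. The end point is therefore the child's own last quantifiable sample, not a fixed time.

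SAP 16.1, Table 1 (identical to Protocol 8.5, Table 3) sets the sampling times by weight in kg. The second entry in a quoted row is whether a pre-dose sample is taken; the rest are hours after dosing:

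- The lightest band reads "5 to < 7 | No | 0.5 | 1 | 2 | 3", so its final sample is at 3 h.
- The middle band adds three later samples to that scheme, and its final sample is at 8 h.
- The heaviest band reads "10 and above | Yes | 0.5 | 1 | 2 | 3 | 4 | 6 | 8 | 12", so its final sample is at 12 h.

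The text agrees with the table: "Children weighing 5 kg to less than 7 kg will have 4 PK samples taken", with 7 and 9 samples in the two heavier bands.

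On reporting, SAP 16.1.1.1 begins "PK parameter data will be descriptively summarized using: number of non-missing observations" and goes on to the arithmetic mean, SD, CV%, median, geometric mean and its 95% CI. Only tmax is given a reduced set of statistics. That section names no grouping. The grouping comes from the general rule in SAP Section 9: "Unless otherwise indicated all analyses will be presented separately for treatment groups", the groups being 1a, 1b, 2, 3, 4a and 4b. SAP 16.1 plans no other PK analysis, so there is no common-window AUC, no extrapolated AUC and no breakdown by weight band.

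SAP 16.1 does say that parameters are calculated where possible and as suits each sampling scheme, and that they are evaluated for children with enough data. It sets no criterion for either.

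**The concern.** An area to 3 h and an area to 12 h are different quantities. If they are averaged in one cell, the result depends on how many children fell in each weight band as well as on how the drug behaves. The artefact has one direction: for the same concentration profile, a shorter window can only give an equal or smaller area, and the shorter windows belong to the lighter children.

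The PK sub-study is meant to describe systemic concentrations in the targeted paediatric age groups, so readers will set the group AUCs side by side. A lower geometric mean in Cohort 3 than in group 1a could then reflect the blood-volume schedule alone, and the table would give no sign of it.

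**Working it through.** **1. The plan's own figures.** Counting the entries in SAP Table 1 gives 4, 7 and 9 samples (the 9 include the pre-dose sample), as the text states. The last times are 3, 8 and 12 h.

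**2. Which groups can mix schemes.** Protocol 5.1 sets a minimum weight of 5.0 kg at 3 to <24 months and 8.0 kg at 2 to 6 years. Protocol Appendix 6 gives typical weights of 6 kg at 3 months, 9 kg at 10 months, 12 kg at 2 years and 15 kg at 4 years. Linear interpolation puts:

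- 7 kg at 3 + (7 − 6)/(9 − 6) × (10 − 3) = 5.3 months
- 10 kg at 10 + (10 − 9)/(12 − 9) × (24 − 10) = 14.7 months

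So Cohort 3, and Cohorts 4a and 4b (3 months to 6 years), can contain all three schemes. Cohort 2 can contain the 8 h and 12 h schemes. Groups 1a and 1b (4 to 6 years) should be almost entirely on the 12 h scheme.

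**3. Size for one child.** The documents give no half-life, tmax or LLOQ, so these are assumptions. Take a one-compartment oral profile, the same for every child, with ke = ln 2 / half-life and ka solved from tmax = ln(ka/ke)/(ka − ke). Then, up to a constant,

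AUC(0–T) = ka/(ka − ke) × [(1 − e^(−ke·T))/ke − (1 − e^(−ka·T))/ka].

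| Half-life, tmax (h) | ke, ka (per h) | AUC0-3 | AUC0-8 | AUC0-12 | 3 h / 12 h | 8 h / 12 h |
|---|---|---|---|---|---|---|
| 1, 0.5 | 0.693, 4.38 | 1.229 | 1.436 | 1.442 | 0.85 | 1.00 |
| 2, 1 | 0.347, 2.19 | 1.674 | 2.671 | 2.832 | 0.59 | 0.94 |
| 3, 2 | 0.231, 0.924 | 1.533 | 3.420 | 3.967 | 0.39 | 0.86 |

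Applying the SAP's trapezoid rule to the scheduled times under wider assumptions (half-life 1 to 4 h, ka 0.8 to 3 per h, LLOQ 0.1 to 5% of Cmax) gives 0.31 to 0.91 for the 3 h scheme and 0.81 to 1.00 for the 8 h scheme.

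**4. Size for a group.** If n3 and n8 of n children are on the short schemes, with individual ratios r3 and r8, the group geometric mean is multiplied by exp[(n3 ln r3 + n8 ln r8)/n]. Cohort 3 plans 5 to 10 PK children; take n = 10 and mid-range ratios r3 = 0.60, r8 = 0.95.

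- Assumed split 2/5/3 across the bands: exp[(2 ln 0.60 + 5 ln 0.95)/10] = 0.88. With (r3, r8) from (0.35, 0.80) to (0.85, 1.00) the range is 0.73 to 0.97.
- Assumed split 0/5/5: exp[(5 ln 0.95)/10] = 0.975. With r8 from 0.80 to 1.00 the range is 0.89 to 1.00.

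**5. With a common window.** For one profile at the scheduled times, AUC0-3h is the same under all three schemes (ratio 1.00), and AUC0-8h is the same under the 8 h and 12 h schemes (ratio 1.00). The artefact disappears.

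**The case against.** The PK objective is the concentration-time profile in a subset, with parameters only where appropriate. Subset sizes rest on feasibility, and no comparison of AUC between ages is planned. The wording about suiting each sampling scheme lets the PK group omit or separate short-scheme AUCs. Individual parameters are listed, and concentrations are summarised and plotted, so the shared 0.5, 1, 2 and 3 h samples can already be compared like for like.

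The worst-affected band may also be nearly empty. A typical child passes 7 kg at about 5 months, and Phase II enrolled only 4 children of 3 to 12 months against 20 of 13 to 24 months (Protocol 4.2.3). The shift may also sit well inside the noise: at an assumed CV of 50 to 100% and n = 10, the 95% CI for a geometric mean runs from about 0.71–1.40 to 0.55–1.81 times the estimate.

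Much of this stands, and it limits the size and importance of the point. It does not remove it. Permission to do what is appropriate is not a rule: the SAP does not say whether a 3 h AUC is dropped, flagged or pooled. Sampling noise is displayed in the confidence interval, whereas truncation is not displayed at all.

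A reader might go further and infer that infant exposure is understated in general. The documents do not support that. Weight sets the window, not age: a child in Cohort 3 of 10 kg or more has the full 12 h schedule, while a child of 2 years or more weighing 8 to <10 kg is on the 8 h scheme. Nor do they support the inference that the sub-study exists to compare exposure between ages, or that group means would be 15 to 61% too low. That last range (1 − 0.85 to 1 − 0.39) belongs to a single child under 7 kg on assumed kinetics.

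**Conclusion.** The point holds as a reporting defect in a descriptive secondary output. Followed as written, the SAP pools areas over unlike windows in Cohorts 3, 4a and 4b, and to a lesser extent Cohort 2, with no rule to prevent it.

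The direction is certain for identical profiles; the size is not. It depends on assumed kinetics and an assumed weight mix: material for a child of 5 to <7 kg, small to moderate at 7 to <10 kg, and absent at 10 kg and above. The group effect is modest unless several children weigh under 7 kg. This is a cheap improvement and has no bearing on the cure-rate analyses.

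**What to change.** In SAP 16.1 and 16.1.1.1:

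1. Present AUC0-t summaries by sampling scheme (3, 8 and 12 h) within each treatment group, and do not pool schemes.
2. Add AUC0-3h for all PK children and AUC0-8h for those of 7 kg and above as supplementary like-for-like measures alongside AUC0-t.
3. Give a rule for samples taken early within the ±10% tolerance. Actual times are used in the calculation, so a nominal 3 h sample may be at 2.7 h and a nominal 8 h sample at 7.2 h. State whether the area is extrapolated to the nominal time or stopped at the actual time and flagged.
4. Say what counts as enough data to report an AUC under each scheme.

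The cost is a partial-AUC setting in the planned PK software and some extra table rows; blood sampling is unchanged. There are two drawbacks. Cells become smaller, and some may not exceed the SAP's N>2 threshold for descriptive statistics, in which case the individual listing has to suffice. AUC0-3h mainly reflects early exposure (as little as 39% of AUC0-12 in the model above) and is sensitive to absorption rate, so it should carry a footnote that it is not a measure of total exposure.

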16.1.1 Presentation of PK Concentration and PK Parameter Data

16.1.1.1 Listings and Tables (PK Analysis Population)

Statistical analyses and descriptive summaries of pharmacokinetic data will be performed on the PK Analysis Population (PKP, as defined in Section 8.2). The following PK tables and listings will be produced:

- a) Descriptive Statistics of PK Concentration Data:
 - PK measurements will be descriptively summarized using: number of non-missing observations (N), arithmetic mean (Mean), standard deviation (SD), coefficient of variation (CV%), minimum (Min), median (Median) and maximum (Max).
 - Descriptive statistics will only be calculated for N>2 in which a measurement of <LLOQ represents a valid measurement

- Descriptive statistics of PK concentration data will be calculated using values with the same precision as the source data and rounded for reporting purposes only.
- The following conventions will be applied when reporting descriptive statistics of PK concentration data:
 - Mean, Min, Median, Max: 3 significant digits
 - SD: 4 significant digits
 - CV%: 1 decimal place

b) Descriptive Statistics of PK Parameter Data

- PK parameter data will be descriptively summarized using: number of non-missing observations (as N), arithmetic mean, standard deviation (SD), coefficient of variation (CV%), minimum, median, maximum, geometric mean (GeoMean), the geometric coefficient of variation (GeoCV) and the 95% confidence interval for the GeoMean (LCI 95% GM, UCI 95% GM). For time to reach maximum observed concentration (t_{max}), only n, minimum, median, and maximum will be reported.
- Descriptive statistics will only be calculated for a PK parameter when $N > 2$.
- PK parameters read directly from the measurements (i.e. C_{max}) will be reported with the same precision as the source data. All other PK parameters will be reported to 3 significant figures. In export datasets, as well as in the SDTM PP domain, PK parameters will be provided with full precision and will not be rounded. Descriptive statistics of PK parameter data will be calculated using full precision values and rounded for reporting purposes only.
- The following conventions will be applied when reporting descriptive statistics of PK parameter data:
 - Mean, Min, Median, Max, GeoMean, 95% CI: 3 significant digits
 - SD: 4 significant digits
 - CV%, GeoCV%: 1 decimal place

16.1.1.2 Graphical Summaries and Individual plots (PK Analysis Population)

- Individual concentration versus time plots; linear and semi-log; using the actual time points by participants, day, analyte, matrix and group; if any post-dose concentrations is <LLOQ the line representing LLOQ will be added to the semi-log plots.
- Overlaid individual concentration versus time plots; linear and semi-log; by analyte, matrix and group; if any post-dose concentrations is <LLOQ the line representing LLOQ will be added to the semi-log plots.
- Mean concentration time plots; linear with standard deviation and semi-log; using scheduled (nominal) time points by day, analyte, matrix and group; if any post-dose

concentration is <LLOQ the line representing LLOQ will be added to the semi-log plots. Error bars should be included only in the linear plots.

17 References

Clinical protocol number **MS200661-0003**

19 Mar 2019 /V1.1 Côte D'Ivoire

20 Feb 2019 /V1.1 Kenya,

11 August 2020/V1.2

18 Appendices

18.1 Appendix A: Planned analyses for IDMC meetings

Refer to the IDMC Charter.

18.2 Appendix B: Prohibited concomitant medications

Prohibited medications, by WHO Drug Dictionary ATC classification:

| Prohibited medications | ATC Code | ATC level |
|--|--|----------------------------|
| Praziquantel and other antihelminthics | P02 | 2 |
| Antimalarials, including chloroquine | P01B | 3 |
| Antiepileptics | N03 | 2 |
| Glucocorticosteroids (systemic) | H02 | 2 |
| Anti-infectives for systemic use | J | 1 |
| Xanthine-containing drugs | C03BD N06BC R03DA R03DB | 4 4 4 4 |
| Anti-retrovirals | J05AB J05AE J05AF J05AG J05AR J05AX | 4 4 4 4 4 4 |

Specific prohibited medications, listed by preferred term:

- Cimetidine
